### **11.4 Analysis of Primary Endpoints**

Overall survival will be analyzed using Kaplan-Meier methods. Patients who have not died at the time of analysis will be censored on the date they were last known to be alive. Median survival and the associated 95% confidence interval will be computed using the Brookmeyer-Crowley method. The estimated survival curve will be generated.

Estimates of 30- and 60-day mortality rates will be computed using Kaplan-Meier methods along with associated two-sided 95% confidence intervals computed using the Brookmeyer-Crowley method.

### **11.5 Analysis of Secondary Endpoints**

Time dependent endpoints, such as remission duration (relapse-free survival) and event-free survival (EFS), will be evaluated using Kaplan-Meier methods; estimates of event rates will be computed and a survival curve generated.

#### *Binary Endpoints*

The response (CR, CRp, CRI, and CR+CRp+CRI) rate and best response (CR, CRp, CRI, and CR+CRp+CRI) rate will be calculated based on the responses achieved as defined in section 8.4. The number of patients who achieve response will be divided by the number of patients in the efficacy population to determine response rate.

Likewise, the morphologic leukemia-free rate will be calculated as the number of patients who achieve morphologic leukemia-free state, as defined in section 8.6, divided by the number patients in the safety population who have at least one evaluable post-randomization bone marrow assessment.

The rate of stem cell transplant will be calculated by the number of patients who have a stem cell transplant divided by the number of patients in the safety population.

### **11.6 Safety Analysis**

Safety data will be analyzed and reported for all patients who receive at least one dose of study drug. Safety data summarized will include hematology, chemistries, vital signs,

adverse events (AEs) and physical examinations. Safety data will be summarized using descriptive statistics.

The number and proportion of patients with reported AEs and SAEs will be summarized by maximum grade. AEs that are related to study drug will be summarized in a separate table.

Laboratory values will be summarized both by actual result and by CTC toxicity grade (for selected laboratory parameters). Summaries of laboratory results at each scheduled time point will reflect the observed value at that time point as well as change from baseline. For selected laboratory parameters, the maximum grade for each patient will be summarized for each type of toxicity; a shift table will reflect baseline toxicity grade versus maximum observed on-treatment toxicity grade.

Vital signs and physical exam data will be summarized at each scheduled time point.

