**Secondary**

- To assess efficacy by response (CR, CRp, CRI, and CR+CRp+CRI) rate, response duration, and Event Free Survival (EFS)
- To assess safety by 30-day mortality, serious adverse events (SAE) and adverse event frequency and severity
- To assess QOL using FACT-LEU
- To assess the relationship of cognitive function to outcome using the Blessed Orientation-Memory-Concentration Test and the Montreal Cognitive Assessment
- To confirm the safety of CPX-351 as a post-remission (consolidation) therapy
- To supplement efficacy assessment by determining the rate of morphologic leukemia-free state (MLFS)

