#### 3.2 Secondary Objectives

- To assess efficacy by response (CR, CRp, CRI, and CR + CRp + CRI) rate and duration and Event Free Survival (EFS)
- To assess safety by 30-day mortality, serious adverse events (SAE) and adverse event frequency and severity
- To assess QOL using FACT-LEU
- To assess the relationship of cognitive function to outcome using the Blessed Orientation-Memory-Concentration Test and the Montreal Cognitive Assessment
- To confirm the safety and practicality of CPX-351 as consolidation therapy
- To supplement efficacy assessment by determining the rate of morphologic leukemia-free state (MLFS)

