## 4.5 Consolidation Therapy

Only patients with confirmed response (CR or CRp or CRi) and who remain fit for additional chemotherapy are eligible for chemotherapy consolidation. Investigators may

use post remission therapy of their choice or they may choose to use CPX-351. Before consolidation treatment can begin, patients need a repeat echocardiogram and labs to evaluate renal and liver function and must fulfill eligibility criteria initiation of treatment. For patients given CPX-351 post remission therapy: prior to starting consolidation, LVEF must be documented to be  $\geq 50\%$  and patients must have recovered to ANC  $> 500/\mu\text{L}$  and platelets  $> 50,000/\mu\text{L}$  within 56 days after last dose of CPX-351. A second consolidation cycle is permitted provided the first consolidation course was well tolerated and repeat echocardiogram shows an LVEF  $> 50\%$  and ANC and platelets have recovered within 56 days of the start of the last consolidation cycle. Up to 2 consolidation courses are permitted. Scheduling and dose of consolidation treatment may be adjusted depending on degree and rate of patient recovery.

Dosing for consolidation:

- CPX-351 at 65  $\text{u}/\text{m}^2$  will be administered on days 1 and 3

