#### 4.6 Follow-up Phase

Patients will be followed at monthly intervals or more frequently depending on clinical circumstances until start of the next salvage treatment, death or for 1 year from date of enrollment. Patients alive and in remission after 1 year will be followed annually or more frequently depending on clinical circumstances for up to 5 years from enrollment. For EFS evaluation, events include: documentation of persistent AML after induction, relapse after achievement of CR/CRp/ CRi, or death. Bone marrow assessments will be performed at any time during follow up when recurrent cytopenias raise the suspicion of AML relapse. After documentation of persistent leukemia or relapse, follow-up for OS will continue. At the start of HSCT or non-protocol AML treatment of any sort or 30-days following the last dose, whichever occurs first, AE data collection will stop.

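### The adverse-event analysis in 11.6 has no consolidation-specific table, so it does not answer the objective to confirm the safety of CPX-351 consolidation

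*Combined protocol and SAP*

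**What the plan says.** The synopsis lists as a secondary objective "To confirm the safety of CPX-351 as a post-remission (consolidation) therapy". Section 3.2 words it as "To confirm the safety and practicality of CPX-351 as consolidation therapy", which adds practicality.

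Section 4.5 limits who can contribute: "Only patients with confirmed response (CR or CRp or CRi) and who remain fit for additional chemotherapy are eligible for chemotherapy consolidation". For CPX-351 it adds conditions on LVEF and count recovery. The agent is optional, since investigators may "use post remission therapy of their choice or they may choose to use CPX-351". On number of courses, "Up to 2 consolidation courses are permitted".

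Section 11.6 sets the safety analysis: "Safety data will be analyzed and reported for all patients who receive at least one dose of study drug". For adverse events, "The number and proportion of patients with reported AEs and SAEs will be summarized by maximum grade", with a separate table for drug-related events. The laboratory shift table compares baseline grade with the worst on-treatment grade. Laboratory values, vital signs and physical examinations are also summarised by scheduled time point.

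Section 11.1.2 lists no consolidation endpoint and 11.5 contains no consolidation analysis. Section 11 says that a SAP may give further detail, but does not promise one.

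**The concern.** Consolidation always follows induction, and it is a different regimen: 4.3 and 4.5 give 100 u/m² on days 1, 3 and 5 for first induction, and 65 u/m² on days 1 and 3 for consolidation. Section 2.4 says that most grade 3/4 events with CPX-351 are tied to prolonged myelosuppression. A patient who reaches consolidation may therefore already have a high grade on record for the toxicities of most interest.

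A table of each patient's worst grade, pooled over everyone dosed, mainly describes induction. If it is the only AE summary produced, the report contains no AE frequency for consolidation, and a reassuring overall table could be cited as having met the objective. Practicality has no stated measure either: nothing asks how many responders started or finished each CPX-351 consolidation course.

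**Working it through.** **1. Match the objective to the analyses.** Sections 11.1.2, 11.5 and 11.6 contain no endpoint, subgroup, denominator or criterion specific to consolidation. AE collection does extend that far: 6.2 requires continual assessment from first dose until 30 days after the Treatment Period, and the Appendix 1 flow sheet applies to each induction and each consolidation. The gap is in the analysis, not in the data.

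**2. What a maximum-grade table shows.** Take a patient with a grade 3 event in induction and the same grade 3 event in consolidation. The table counts that patient once, at grade 3, exactly as if consolidation had been uneventful. Let *p* be the share of consolidated patients who already had that term at that grade or worse in induction, and assume that induction and consolidation events are independent. The share of consolidation events that changes the table is then 1 − *p*:

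- *p* = 0.20: 80%
- *p* = 0.50: 50%
- *p* = 0.635: 36.5%

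The last value borrows the 63.5% febrile neutropenia frequency reported in 2.4 for the CPX-351 arm of the earlier Phase II study. It is an illustration, because that figure is not specific to induction in patients who went on to consolidation.

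**3. The plan's own safety precision.** Section 11.2 says that, with 30 patients, the one-sided 95% exact interval for 30- or 60-day mortality has a maximum width below 19%. Taking the Clopper-Pearson upper limit minus *x*/30 over all *x*, the maximum is 16.6%, at *x* = 11. The largest two-sided 95% half-width is 18.7%. The statement holds, but it concerns mortality in all 30 patients. No precision is given for consolidation.

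**4. How many patients inform the objective.** Inputs: 30 patients (11.2) and a CR+CRi rate of 47.7% (2.4, CPX-351 arm of the phase 3 trial). Expected responders: 30 × 0.477 = 14.3. The documents do not give the share who would receive CPX-351 consolidation, so I vary it from 33% to 100%. Formulas: zero-event one-sided 95% upper limit 1 − 0.05^(1/*n*); chance of seeing at least one event at a true rate of 10%, 1 − 0.9^*n*.

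| Share of responders | *n* | Upper limit, 0 events | Maximum one-sided width | Chance of ≥1 event at 10% |
|---|---|---|---|---|
| 33% | 14.3 × 0.33 ≈ 5 | 45.1% | 45.7% | 41% |
| 50% | 14.3 × 0.50 ≈ 7 | 34.8% | 37.8% | 52% |
| 75% | 14.3 × 0.75 ≈ 11 | 23.8% | 29.2% | 69% |
| 100% | 14.3 × 1.00 ≈ 14 | 19.3% | 25.4% | 77% |

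For comparison, zero events in all 30 patients would give an upper limit of 9.5%.

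**The case against.** The strongest reply is that this is one secondary objective in a 30-patient study whose analyses are described as primarily descriptive. It touches neither primary endpoint nor any stopping rule, and the missing table can be produced at any time from AE and course dates. That is fair as to weight. It does not supply the table, and a SAP that may or may not be written cannot be relied on for it.

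Other data do bear on consolidation. ECG is scheduled by course and LVEF before each consolidation. The synopsis lists time to hematologic recovery and prolonged cytopenias. Section 9.2.4 puts grade 3 or higher AEs and all SAEs on a cumulative list for the IRB, and 10.4 separates induction from consolidation chemotherapy for resource use. These help, but the cardiac measures cover one organ system, a regulatory listing is not a rate, and 11.6 does not ask for time-point summaries by course even though the flow sheet reuses the same day numbers in every course.

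Some stronger readings are tempting, and the documents do not support them:

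- *The objective cannot be answered.* AEs are collected through consolidation, so a different table answers it descriptively.
- *11.6 takes the maximum over all courses.* That is the natural reading because no split is given, but the section does not say so.
- *All consolidation toxicity is hidden.* Masking needs an equal or worse earlier grade, and for the same term if the maximum is taken per term. A new type of event would still appear.
- *Optional, selected use defeats the objective.* Selection limits generalisation and comparison with other therapy; it does not prevent a description of the patients treated.
- *Consolidation rates are diluted by dividing by 30.* The plan computes no such rate.
- *Transplant removes about a third of responders.* The 34% in 2.4 is among all CPX-351 patients, and nothing says that transplanted patients skip consolidation, so I make no such deduction.

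Section 4.6 stops AE collection "At the start of HSCT or non-protocol AML treatment of any sort" or 30 days after the last dose, whichever is first. If anything, that helps to keep events from other post-remission therapy out of a CPX-351 consolidation table.

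**Conclusion.** The concern holds as a mismatch between an objective and its analysis. As written, 11.6 produces no AE or SAE result for CPX-351 consolidation, and its maximum-grade and shift tables can conceal consolidation events in patients with equal or worse induction grades. How much is concealed depends on an overlap that the documents do not give.

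Even with the right table, the evidence will be thin: about 5 to 14 patients, with a zero-event upper limit of about 45% to 19%. This rests on the 47.7% response rate carrying over from the phase 3 trial and on the assumed 33% to 100% uptake. Numbers of that size support describing safety in selected recipients, not confirming it. No figure stated in the plan is wrong on this point.

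**What to change.** In 11.6:

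- Tabulate AEs and SAEs separately for induction and for CPX-351 consolidation. For consolidation, count events from consolidation Day 1 and use as denominator the patients who received at least one CPX-351 consolidation dose.
- Present the laboratory shift tables by the same two phases, and state which baseline the consolidation table uses.
- Report how many responders received and completed each CPX-351 consolidation course, and how many had other post-remission therapy or HSCT. This gives practicality a measure.

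In 3.2 and the synopsis, replace *confirm* with *describe*.

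No dose, schedule, eligibility rule or sample size changes. The cost is a few extra tables from AE and course dates that the study should already hold, and a more modest claim with wide intervals.

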## **11.7 Data Safety Monitoring Board (DSMB)**

Weill Cornell Medical College requires that all research approved by the WCMC IRB include an appropriate plan for the monitoring of data to ensure the safety of human subjects. Research supported by Federal agencies will be monitored according to all regulations and guidelines of the relevant Federal agency.

The WCMC Data and Safety Monitoring Board (DSMB) will review the IRB approved protocol, informed consent documents, and data and safety monitoring plan prior to study initiation. During the course of the study, the DSMB will perform safety analysis as outlined in 4.2 after 15 subjects have enrolled.

After the initial safety analysis period, the DSMB will review the cumulative study data semiannually to evaluate safety, efficacy, study conduct, and scientific validity and integrity of the trial. In particular, the results of the Day 30 echocardiogram will be included in the DSMB Periodic Reports. The WCMC DSMB may also convene as needed if stopping criteria are met or other safety issues arise that the Principal Investigator and/or IRB would like the WCMC DSMB to address. The study PI will submit all written DSMB recommendations to the IRB upon receipt.

# **12 Administrative, Regulatory and Ethical Issues**

## **12.1 Direct Access to Source Documents**

Source data is all information, original records of clinical findings, observations, or other activities in a clinical trial necessary for the reconstruction and evaluation of the trial. Source data are contained in source documents. Examples of these original documents and data records include but are not limited to: hospital records, clinical and office charts, laboratory notes, memoranda, patients' diaries or evaluation checklists, pharmacy dispensing records, recorded data from automated instruments, copies or transcriptions

certified after verification as being accurate and complete, microfiches, photographic negatives, microfilm or magnetic media, x-rays, patient files, and records kept at the pharmacy, at the laboratories, and at medico-technical departments involved in the clinical trial. All data will be collected and stored on a computerized database using a REDCAP program.

Case report forms, all copies of test results, and study-related regulatory documents [e.g., Informed Consents, Institutional Review Board (IRB)/Ethics Committee (EC) approvals/correspondence, etc.] must be available at all times for regulatory agency inspection and review by the sponsor or its designee. During the periodic site monitoring visits, the source documents will be verified against data entered onto the CRF in order to assure that all data is accurately and completely reflected on the patient's CRF.

## **12.2 Study Monitoring and Quality Inspections/Audits**

This study will be monitored by the WCM PI and/or research team according to GCP/ICH guidelines. An internal site initiation visit will be held prior to initiation of patient enrollment. The protocol, CRFs, study drug supplies, and relevant procedures will be explained in detail at the site visit. Subsequent to patient enrollment, the WCM PI and/or research team will review the CRFs and source documents to ensure that the study is conducted according to the protocol and GCP/ICH guidelines.

To ensure compliance with GCP/ICH guidelines and all applicable regulatory requirements, WCM PI and/or research team may conduct an internal quality assurance audit. Regulatory agencies may also conduct a regulatory inspection of this study. Such audits or inspections can occur at any time during or after completion of the study. If audits or inspections occur, the WCM PI and WCM's research team agree to allow the auditor/inspector direct access to all relevant documents and to allocate his/her time and the time of his/her staff to the auditor/inspector to discuss findings and any relevant issues.

## **12.3 Ethics**

This study will be conducted in accordance with local regulations, GCP, ICH guidelines and the Declaration of Helsinki. The WCM PI will be responsible for the overall conduct of the clinical trial for the site and will be responsible for ensuring the trial is conducted according to the protocol and all regulatory requirements and IRB/EC regulations.

## **12.4 Adherence to the Protocol**

Except for a change that is intended to eliminate an immediate hazard to patients, the approved protocol will be conducted as described. If a change in the conduct is made to eliminate an immediate hazard, the FDA and IRB/EC are notified immediately.

Deviations from the protocol will be considered in two categories, Protocol Violations and Protocol Deviations. Protocol Violations include patients who are not eligible according to the inclusion/exclusion criteria in effect at the time of registration. Protocol Deviations include other non-compliance with the protocol, such as missing or skipped procedures or

evaluations, evaluations performed outside given window, incorrect administration of investigational product, etc.

## **12.5 Protocol Revisions**

All revisions must be discussed with, and be prepared by, the WCM PI. If the revision is an Administrative Letter, the investigator should submit it to the IRB/EC and FDA for their information. If the revision is an Amendment, it will be signed by the WCM PI. The WCM PI must submit the Amendment to the IRB/EC for review and approval prior to implementation. Documentation of approval signed by the Chairperson or designee of the IRB/EC must be sent to the FDA.

If an Amendment substantially alters the study design or increases the potential risk to the patient: (1) the consent form must be revised and submitted to the IRB/EC for review and approval; (2) the revised form must be used to obtain consent from patients currently enrolled in the study if they are affected by the Amendment; and (3) the new form must be used to obtain consent from new patients prior to enrollment. The revised consent form must then also be submitted to the FDA for review and approval.

All revisions will be sent to the national competent authorities in North America.

## **12.6 Retention of Patient Records and Study Files**

CRFs and other reports (e.g., investigator trial files, source documents, original, signed/dated informed consent forms) pertaining to this clinical investigation must be maintained for a minimum of 2 years.

## **12.7 Patient Confidentiality**

The WCM PI and research team will preserve the confidentiality of all patients taking part in this trial. In the event of patient names inadvertently appearing on the trial documentation, this information will not be entered into the computer database for this trial. The WCM PI and research team will seek access to clinical information only after approval to do so has been given by the patient and the relevant authorities. The data from this trial may be used in publications and submissions to regulatory authorities.

Information about study patients will be kept confidential and managed according to the requirements of the Health Insurance Portability and Accountability Act (HIPAA). Those regulations require a signed patient authorization informing the patient of the following:  
What protected health information (PHI) will be collected from patients in this study  
Who will have access to that information and why  
Who will use or disclose that information

### **The rights of a research patient to revoke their authorization for use of their PHI:**

In the event that a patient revokes authorization to collect or use PHI, the Investigator, by regulation, retains the ability to use all information collected prior to the revocation of patient authorization. For patients that have revoked authorization to collect or use PHI,

attempts should be made to obtain permission to collect at least vital status (i.e. that the patient is/is not alive) at the end of their scheduled study period.

## 12.8 Informed Consent

Patients will be required to sign a statement of informed consent that meets the requirements of the US Code of Federal Regulations (21 CFR 50), Canadian regulations, local regulations, ICH guidelines and the IRB/EC of the study center. The medical record will include a statement that written informed consent was obtained before the patient was enrolled in the study and the date written consent was obtained.

Members of the treating team will review the nature of the study, its purpose, the procedures involved, the expected duration, the potential risks and benefits and alternative therapies including best supportive care. Patients must be informed that participation in the study is voluntary, he/she may withdraw from the study at any time and withdrawal from the study will not affect his/her subsequent medical treatment or relationship with the treating physician. Financial costs that will or may be incurred as a result of participation in the study, as well as the efforts to maintain patient confidentiality will also be discussed.

This consent must be witnessed and dated and retained by the WCM PI as part of the study records. A copy of the informed consent form must be given to the patient. In the event the patient is re-screened, the patient is not required to sign another informed consent form unless the patient is re-screened more than 30 days from the previous informed consent form signature date.

If an Experimental Subject's Bill of Rights is applicable in the Investigator's US state, that form must also be prepared and signed by each patient and retained as a part of the required study records. A copy of the Bill of Rights must be given to the patient or the patient's legally authorized representative.

A copy of the IRB approved consent form must be submitted to the FDA and Jazz Pharmaceuticals, Inc. prior to shipment of drug supplies to WCM. Each patient's signed informed consent must be kept on file by the Investigator for regulatory authority inspection at any time.

For all US sites, the HIPAA Privacy Rule Authorization language must be included in the Informed Consent/authorization form (or a separate authorization document) and approved by the IRB (or Privacy Board). The elements of the HIPAA Privacy Rule Authorization are found in APPENDIX 5: Elements of the HIPAA Privacy Rule Authorization.

The Declaration of Helsinki, as amended, recommendations (2008 version), guiding doctors in clinical research must be signed by the Investigator and returned to the Sponsor or its designee. A copy must also be kept on file by the Investigator.

The IRB/EC of an institution must approve the consent form document to be used at that center prior to its local activation; changes to the consent form during the course of the study will also require IRB/EC notification/approval.

The following elements must appear in the consent form: a description of the purpose of the study (indication, that the drug is investigational); potential side effects; potential benefits; study design; voluntary participation; and confidentiality. It is essential that the consent form contain a clear statement that gives permission for 1) information to be sent to and 2) source medical records to be reviewed by the Sponsor and other agencies as necessary.

